1 INTRODUCTION

This is an addendum to both the final statistical analysis plan (SAP) Version 6.0, dated 13th April 2022, and the following key file notes (NTF) which were agreed prior to study unblinding:

- SOP-CLIN-16-FORM-NTF_muscle_strength_SIGNED, dated 4th May 2022
- SOP-CLIN-16-FORM-NTF_hardcoding_07_FE, dated 9th May 2022
- SOP-CLIN-16-FORM-NTF_hardcoding_17_FE, dated 4th May 2022
- SOP-CLIN-16-FORM-NTF_hardcoding_19_FE, dated 11th May 2022
- SOP-CLIN-16-FORM-NTF_hardcoding_21_FE, dated 12th May 2022
- SOP-CLIN-16-FORM-NTF_hardcoding_24_FE, dated 18th May 2022
- SOP-CLIN-16-FORM-NTF_hardcoding_30_FE, dated 7th May 2022
- SOP-CLIN-16-FORM-NTF_hardcoding_38_FE, dated 5th May 2022
- SOP-CLIN-16-FORM-NTF_PODCI_SIGNED, dated 23rd May 2022

This addendum documents key changes, corrections or further clarification regarding specific derivations and analyses described in the SAP or file notes following database lock. Full details of the changes and the reasons for these are detailed below.

2 CHANGES TO THE FINAL SAP

2.1 Change 1

According to the SAP Sections 4.3.2 and 4.4.2, for the Paediatric Outcomes Data Collection Instrument (PODCI) endpoint, change from baseline over time for raw and standardised subscale scores are to be presented and analysed separately for 'parent' or 'self' evaluator. However, on review of the data following database lock and prior to unblinding, it was confirmed that there are a number of cases where a subject has completed a mixture of questionnaires by different evaluators from screening to end of study. Unfortunately, the SAP does not cover this type of scenario.

Italfarmaco and Veristat discussed possible solutions with consideration that a subject will only have a baseline questionnaire completed for one type of evaluator even though this may differ from the evaluator for the post-baseline visit. In order to avoid limitation to only subjects with consistent evaluator across baseline and post-baseline for calculating change from baseline values, a pooled approach has been identified. This was supported by the assumption that scores from questionnaires completed by 'self' where the subject is <10 years of age are considered not fully reliable. However, scores from questionnaires completed by 'self' where the subject is >=10 years old can be considered reliable and comparable to scores from questionnaires completed by 'parent'.

In the data we will have a mixture of questionnaires completed by: 'Parent', 'Self >=10 years', 'Self <10 years', 'Missing' (where missing evaluator applies to completely imputed results where the assessment/visit was not done). Therefore, the approach will be as follows.

Questionnaires will be divided into two groups based on the type of evaluator:

- Group 1: 'Parent' + ('Self' >=10 years old)
- Group 2: 'Missing' + ('Self' <10 years old)

Group 1 non-missing subscale scores will remain unchanged. Group 1 missing subscale scores will be imputed as described in the SAP Sections 4.4.4.1, 4.4.4.2 and 7.5.8 using the approach for Class 1 missing data based on Group 1 non-missing results (for the respective subscale, visit, treatment, concomitant steroid and target/off-target group).

Group 2 subscale scores (both non-missing or missing scores) will be replaced with imputed values using the same approach for Class 1 missing data but also based on Group 1 non-missing results (for the respective subscale, visit, treatment, concomitant steroid and target/off-target group), rather than Group 2 non-missing results.

All values (Group 1 and Group 2 non-missing and imputed values) will then be analysed together as equivalent measures, i.e., all are included in calculation of change from baseline and summaries/analyses. The analysis tables will be presented based on these values without distinction between different evaluators. The amended table, figure and listing (TFL) shells for these presentations are supplied in the separate document 'TFL Shells Addendum 1'. These replace the following equivalent planned outputs in the TFL Shells Final 4.0: Tables 14.2.8.1.1 to 14.2.8.5.6 and Listings 16.2.6.8.1 to 16.2.6.8.4.

Reason for the change

As detailed above, this change has been implemented as the SAP defined approach did not allow for the mixture of questionnaires completed by different evaluators per subject as collected in the data.

2.2 Change 2

Section 7.4.1 of the SAP (PODCI Completed by Parent) includes the following instruction when describing the required derivations for some of subscale scores on the parent completed questionnaires: "any item rated "5" (Too young for this activity) is considered missing and is not added to the scale".

It was noted that for some questions on the parent completed questionnaire, the response indicating that the subject was too young for the activity is given a different number, for example '6' rather than '5'. In addition, there are some questions where the response is phrased slightly differently, for example: "Child is too young". Affected questions are questions 10 to 14 used for the 'Happiness' subscale.

To accommodate these differences, the approach was therefore corrected to consider any item as missing for subscale calculation if the text response contains the phrase 'too young' (regardless of the number of the response or exact phrasing of the full response). This was agreed to be the intention of the SAP instructions.

Reason for the change

The differences between question responses regarding 'too young' were overlooked in the SAP instructions for calculating subscale scores on the parent completed PODCI questionnaire. This change was implemented in order to correct this and ensure that any such responses were handled consistently in the scoring.

2.3 Change 3

Section 7.4.2.3 of the SAP (Sports and Physical Function) describes the derivations required for calculating the sports and physical function subscale scores for the subject completed PODCI questionnaires. This includes the following instruction:

- Q50 is recoded to missing if (Q50 = 4 and Q59 = 1)

However, it was noted that the question 59 relates to the response regarding 'Doing things with friends' limited by 'Health', whereas it was agreed that this instruction should instead refer to question 56 which is related to 'participating in sports' limited by 'Activity not in season'.

Therefore, this derivation was corrected to the following:

- Q50 is recoded to missing if (Q50 = 4 and Q56 = 1).

Reason for the change

This was a correction due to an erroneous question reference in the SAP instructions.

2.4 Change 4

It was noted that some of the rules for imputation in the SAP Section 7.5.13 (Time to Persistent Loss of Standing (Baseline Through End of Study)) are no longer relevant given the approach to impute individual missing North Star Ambulatory Assessment (NSAA) item scores as described in the SAP Section 7.5.4 (Physical Function as Measured by NSAA).

The rules for imputation of the NSAA rise from floor item in Section 7.5.13 were written to handle the situation where there are remaining missing individual NSAA item scores prior to deriving the time to persistent loss of standing endpoint. However, after this text was written and prior to SAP finalisation and database lock, the approach in Section 7.5.4 was updated to ensure that all item scores will be populated following imputation of the NSAA endpoint. Therefore, there is no requirement to apply the additional rule to carry forward item scores as described in Section 7.5.13. Instead, the decision was taken to use the values already imputed per the rules in Section 7.5.4 so that this is consistent.

It should be noted that, in some cases, the imputation rules in Section 7.5.4 mean that the rise from floor item score could be imputed to zero but without distinction between '0a' or '0b'. In these cases, the following approach was agreed:

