#### **5.1.2 Secondary Objectives**

The secondary objectives of this study are:

- To assess the safety and tolerability of givinostat versus placebo administered chronically in DMD subjects.
- To evaluate the PK profile of givinostat administered chronically in DMD subjects
- To evaluate the impact on quality of life and activities of daily living of givinostat versus placebo administered chronically.

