4.4.4 Handling of Missing Data

4.4.4.1 Classification and Imputation

For the efficacy analyses, any missing data for continuous values for a subject will be classified as follows:

1. the subject has missing data due to reasons other than being non-ambulatory or physically unable to perform the test / assessment
2. the subject has missing data due to being either non-ambulatory or otherwise physically unable to perform the test / assessment.

Any missing values classified as 1 will be imputed using the mean of all non-missing values for the respective measurement and timepoint across all subjects randomised to the respective treatment and in the respective concomitant steroid stratum and Group (i.e. Group A, target population or Group B, off-target population).

Any missing values classified as 2 will be imputed by setting the value to zero or to twice the maximum non-missing value recorded across all subjects depending on the directionality of the test.

In all cases, imputation of any data classified as 1 will be completed first, followed by imputation of any data classified as 2.

Classification and imputation of missing data will be completed prior to any transformation of the data for analysis. For example transformation of the timed function test results for presentation of velocity or any log transformation applied as needed (per Section 4.4.2).

For binary or time to event variables where missing data means that the binary response or time to event cannot be determined, the missing data from which the variable is derived (e.g. 6MWT values) will first be classified and imputed, as described above, in order to then derive the binary response or the time to event. Exceptions to this are where the criteria for deriving the binary response themselves refer to presence of missing data, for example loss of ambulation. The classification described above will be used for the relevant missing data in these cases in order to confirm physical inability to complete the respective test. Further details are given below regarding the rules for derivation of the binary endpoints in the presence of missing data.

For the NSAA assessment, where the total score is a sum of ordinal item scores, imputation of Class 1 and Class 2 data will follow a different approach as defined in Appendix 7.5.4.

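### Observed PODCI self-reports from boys under 10 are replaced by a cell mean and analysed as full observations, so the standard error is too small wherever 18-month scores are replaced

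*SAP*

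**What the plan says.** SAP Addendum section 2.1 sorts PODCI questionnaires by who completed them. Parent reports and self-reports from age 10 form Group 1. The rest are defined as "Group 2: 'Missing' + ('Self' <10 years old". The reason given is that scores self-completed "where the subject is <10 years of age are considered not fully reliable", together with the wish not to lose boys whose evaluator changed between baseline and follow-up.

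The rule is then that Group 2 scores, observed as well as missing, "will be replaced with imputed values using the same approach for Class 1 missing data but also based on Group 1 non-missing results". The mean is taken from Group 1 scores, "for the respective subscale, visit, treatment, concomitant steroid and target/off-target group), rather than Group 2 non-missing results". The Class 1 approach is defined in SAP 4.4.4.1: "Any missing values classified as 1 will be imputed using the mean of all non-missing values for the respective measurement and timepoint". It is a single fixed value with no random draw. All values, real and imputed, "will then be analysed together as equivalent measures, i.e., all are included in calculation of change from baseline and summaries/analyses".

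SAP 4.4.2 analyses PODCI by ANCOVA of the change to 18 months, with treatment, steroid stratum, age and baseline score in the model. Protocol 5.2.5 and SAP 4.3 make PODCI exploratory, with nominal p-values. It nevertheless serves a secondary objective in Protocol 5.1.2: "To evaluate the impact on quality of life and activities of daily living of givinostat versus placebo administered chronically". Protocol Table 6 schedules no other quality-of-life instrument.

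**The concern.** Doubt about self-report in young boys is a reason to disregard those scores. It is no reason to put a constant in their place and count the constant as data. The fill-in value is the mean of the boy's own arm and stratum, and both arm and stratum are terms in the ANCOVA. A replaced 18-month score therefore adds almost nothing to the residual variance but counts as a full subject. The model sees a smaller spread and a larger sample than exist.

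At stake are the confidence intervals and p-values for the five PODCI subscales and the global score. No safeguard covers them: the tipping-point analysis in SAP 4.4.4.3 is for the stair-climb endpoint only, and neither the SAP nor the addendum gives a variance correction, multiple imputation or missing-data sensitivity analysis for PODCI. The addendum also presents the analysis tables without distinguishing evaluators, so the effect cannot be judged from them.

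**Working it through.** The plan states no PODCI standard deviation, power or count of replaced questionnaires, so there is no figure of its own to reproduce.

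**Formula.** Let an arm have n boys with 18-month score variance σ², and let a share f of those scores be filled with the mean of the rest.
- True variance of the arm mean: only (1 − f)n scores carry information, so it is σ² / [(1 − f)n].
- Variance the model reports: the filled scores add no spread, so the estimated σ² is about (1 − f)σ², and it is divided by n, giving (1 − f)σ² / n.
- The ratio of the two is (1 − f)², so model SE / true SE ≈ 1 − f.
- Actual two-sided error of a nominal 5% test ≈ 2 × [1 − Φ(1.96 × (1 − f))]. At f = 20%, 1.96 × 0.80 = 1.568, which gives 11.7%.

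**Simulation check.** From the documents: 110 boys in the target population, 2:1 allocation, four steroid strata, ANCOVA with baseline, age and stratum. Assumed: no treatment effect, unit SD, baseline-to-18-month correlation 0.6, stratum shares 35/20/25/20%; 4,000 trials per setting.

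| f at 18 months | SE ratio, formula | Error, formula | SE ratio, simulated (both visits / 18 months only) | Error, simulated (both visits / 18 months only) |
|---|---|---|---|---|
| 5% | 0.95 | 6.3% | not run | not run |
| 10% | 0.90 | 7.8% | 0.88 / 0.89 | 8.5% / 8.3% |
| 20% | 0.80 | 11.7% | 0.78 / 0.77 | 12.1% / 12.2% |
| 30% | 0.70 | 17.0% | 0.67 / 0.69 | 18.2% / 16.8% |

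At f = 30%, a correlation of 0.3 or 0.8 gives a ratio of 0.66 to 0.70, so this assumption matters little.

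**Baseline only.** Replacing 10% to 50% of baseline scores and no 18-month scores gives ratios of 0.92 to 0.99 and error of 5.0% to 7.3%. The damage comes from the 18-month scores.

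**Replacement driven by age.** A boy who is 10 − 1.5 = 8.5 years or older at baseline is at least 10 at month 18, so his 18-month self-report is kept. With baseline ages assumed uniform from 6 to 13 and 25%, 50% or 75% of questionnaires self-completed, about 9%, 18% and 27% of 18-month scores are replaced. The SE ratios are 0.89, 0.80 and 0.73, and the errors 8.2%, 11.4% and 15.1% (5,000 trials each).

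**After the fix.** With Group 2 scores left missing and only observed Group 1 pairs analysed:
- at 20%, model SE is 0.186 SD against a true 0.188, error 5.1%; the addendum rule at both visits gives 0.147 against 0.188, error 12.1%;
- at 30%, model SE is 0.199 against 0.204, error 5.3%; the addendum rule gives 0.138 against 0.205, error 18.2%.

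The true SE is practically the same under both approaches, so replacement adds no information and only makes the reported SE smaller.

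**The case against.** Several counter-arguments have force.

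- **PODCI is exploratory.** This stands. No alpha is spent on it, and inflated error for a formal claim cannot be inferred. But a nominal 95% interval should still cover about 95%.
- **The addendum did not invent the method.** Also right. SAP 4.4.4.2 and 7.5.8 already fill every missing PODCI score with the Class 1 mean. If the 8% dropout assumed in SAP 2.5 were all filled this way, the formula gives 2 × [1 − Φ(1.96 × 0.92)] = 7.1% before any self-report is touched. Adding a further 10% of replaced self-reports makes f = 18% and the error 2 × [1 − Φ(1.96 × 0.82)] = 10.8%. The addendum's own contribution is that increment. It also follows that setting the scores to missing, with nothing else changed, would give exactly the addendum's result.
- **The share may be small.** Protocol 10.2 has the PODCI administered to the parent or guardian, although SAP 4.3.2 allows self-completion. At f = 2% the error is only 5.5%. The PODCI file note of 23 May 2022 listed in the addendum is not among these documents and may give the count.
- **Imputed efficacy values are flagged in listings** (SAP 2.8). This helps traceability but does not correct the intervals.

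A reader might also infer that the choice followed the results, or that the estimated treatment effect is biased. The documents support neither. The addendum places the data review after database lock but before unblinding, and the calculations show an understated standard error, not a shifted estimate.

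**Conclusion.** The point holds in a limited form. Replacing observed 18-month self-reports with a cell mean and analysing them as full observations makes the PODCI standard errors too small, by a factor of about (1 − f), and the confidence intervals and p-values too favourable. The direction is certain whenever any 18-month score is replaced. The size is conditional on f, which the documents do not give. The error rates also rest on the simulation assumptions above, to which they are not very sensitive.

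Two stronger readings fail. The factor (1 − f) does not apply to the share of all scores replaced across visits, because baseline-only replacement has little effect. And no primary or key secondary conclusion is touched. The matter deserves correction because the affected intervals are the trial's only quantitative evidence on quality of life.

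**What to change.** Amend the addendum as follows:

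1. Set self-reports from boys under 10 to missing and exempt PODCI from Class 1 mean imputation. Both parts are needed.
2. Analyse the observed Group 1 scores by ANCOVA, or by MMRM using months 12 and 18. Alternatively, use multiple imputation within arm, conditional on baseline, age and steroid stratum.
3. Report the number of scores set to missing, by arm and visit.
4. Add one sensitivity analysis that keeps all observed scores, including self-reports under 10. An evaluator covariate is best avoided, since it is not well defined when the evaluator changes between baseline and follow-up.

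The cost is a wording change, a re-run of the PODCI tables and wider intervals. In the simulation the reported SE rises by a factor of 0.186 / 0.147 = 1.27 at 20% replaced and 0.199 / 0.138 = 1.44 at 30%. That widening restores roughly correct coverage.

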4.4.2 Modelling Methods

All efficacy analyses will be conducted in the target population. Formal analysis will be conducted as described in this Section for the following in the target population: the primary efficacy endpoint at 18 months, all key secondary efficacy endpoints at 18 months. All other analyses (i.e. for different endpoints or timepoints in the target population, sensitivity or supplementary analyses, or any efficacy analyses later added for the overall population) will be supportive only and will not be subject to alpha control. Therefore, nominal p-values will be presented.

The change from baseline to 18 months after treatment with givinostat or placebo for the continuous efficacy variables described in Sections 4.1, 4.2 and 4.3 will be analysed using an analysis of covariance (ANCOVA). Note that the ANCOVA analysis of muscle strength will be performed on the normalised muscle strength variable (measured in N/Kg) only. In addition, the ANCOVA analysis of NSAA will be performed on the total NSAA score only, ANCOVA analysis of PODCI scores will be performed

on the standardised scores only (for each subscale and the global function scale as completed by subject and parent), and ANCOVA analysis of MRI parameters will be performed for the fat fraction results only. In each instance, the dependent variable will be the outcome being modelled and terms for the corresponding baseline value and re-derived age at first dose (in years and months) will be included as independent covariates in the model, with randomised treatment group and concomitant steroid use (according to the 4 possible strata) included as independent classification factors. Where the dependent variable is not the muscle strength test, MRS VL MFF, PODCI score or MRI parameters, additional covariates will also be included in the model for the following baseline values (where not already included): 4SC, time to rise from floor, time to run/walk 10 metres, distance walked in 6 minutes (for the analysis of percent predicted 6MWT, this will be replaced with baseline percent predicted distance walked in 6 minutes).

Least squares means and associated 2-sided CIs will be estimated for givinostat and placebo. The treatment effect, being the difference in least squares means (givinostat-placebo), will be presented along with the associated 2-sided CI and p-value.

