The rules for classifying missing data from the responses on the eCRF and any additional considerations for imputation are given in Appendix 7.5 for each respective endpoint. Unless otherwise stated, only the value of interest for analysis will be classified and imputed. For example, the 'duration' for the 4SC assessment will be imputed but not the 4-stair ascent grading.

Note that missing data at any scheduled timepoint should be imputed according to the above rules. This includes any scheduled timepoints after a subject withdraws early. In these cases, where the final assessment prior to withdrawal was missing and determined to be Class 2 missing data, all missing assessments post withdrawal will also be considered Class 2. Otherwise, these will be considered Class 1. Note that where this applies to an NSAA assessment, 'Class 1' will refer to the scenario where

'Was assessment attempted?' = 'No'. Where a date of assessment is required, the predicted date for imputed timepoints post withdrawal will be used. The same approach will be followed for any completely missing visits prior to withdrawal or completing the study, where no information has been entered into the respective CRF assessment page indicating whether or not it was performed.

Where data entered into the CRF for an assessment are ambiguous such that they do not reflect any of the expected responses outlined in Appendix 7.5 and therefore missing data cannot be classified, a worst case approach will be followed and the missing data will be assumed Class 2.

A review will be performed at the BDRM to confirm correct classification of missing data. This may identify data entered into the CRF assessment page which comply with Appendix 7.5 but additional information is available to contradict the classification (for example in comments). Any such cases will be assessed on a case by case basis to determine the appropriate classification to be applied.

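### SAP Addendum Change 1 fills pre-randomisation PODCI scores from the boy's own treatment arm, which weakens the baseline adjustment and understates its standard error

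*SAP*

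**What the plan says.** Protocol Table 6 and section 9.1.1 place the first PODCI at Visit 1. Section 9.1.2 does not list it at randomisation, so screening is the only pre-dose assessment.

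SAP Addendum 2.1 deals with cases where "a subject has completed a mixture of questionnaires by different evaluators from screening to end of study", and notes that "a subject will only have a baseline questionnaire completed for one type of evaluator". Group 1 is parent-completed forms plus self-completed forms at age 10 or over. Group 2 is self-completed forms under 10 plus forms with no evaluator. The rule is: "Group 2 subscale scores (both non-missing or missing scores) will be replaced with imputed values using the same approach for Class 1 missing data". The donor mean is "based on Group 1 non-missing results (for the respective subscale, visit, treatment, concomitant steroid and target/off-target group), rather than Group 2 non-missing results". Filled and genuine values are then treated alike: "all are included in calculation of change from baseline and summaries/analyses".

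The parent SAP does not exempt baseline. Section 4.4.4.1 says that "missing data at any scheduled timepoint should be imputed according to the above rules", and 4.4.4.2 imputes before the change from baseline is taken. Under 4.4.2, "terms for the corresponding baseline value and re-derived age at first dose (in years and months) will be included as independent covariates". Sections 7.5.13 and 7.5.14 contain special rules for baseline data of other endpoints; 7.5.8, on PODCI, contains none.

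**The concern.** A score taken before randomisation cannot depend on treatment. Here it can: a boy under 10 who filled in his own screening form loses that recorded score and receives the mean of Group 1 boys in the arm to which he was later assigned. Whatever chance difference the Group 1 boys show between arms at screening is thereby attributed to the replaced boys too, and the ANCOVA corrects for an imbalance that was never observed in them.

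This is separate from the filling of post-baseline scores. It remains when the month-18 score is genuine, for example when a boy aged 9 at screening is over 10 at month 18, or when the parent answers then.

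At stake are the precision and the nominal p-value of the only quality-of-life instrument. Quality of life is a stated secondary objective.

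**Working it through.** The plan gives no PODCI precision or power, so there is no figure to reproduce.

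**Inputs.** From the documents: 110 boys in the target population, 2:1 allocation, four steroid strata, ANCOVA on change with own baseline as covariate. Assumed: share of screening scores replaced m (20-60%), baseline to month-18 correlation ρ (0.5-0.7), replacement unrelated to score, month-18 scores all observed.

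**Step 1: what the model estimates.** ANCOVA on change with the same baseline as covariate gives the same treatment estimate as ANCOVA on the month-18 score Y. With arm-mean filling, each arm's mean baseline equals its Group 1 mean, so the estimate is

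(Ȳ_T − Ȳ_C) − b(X̄_obs,T − X̄_obs,C).

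**Step 2: true variance**, relative to no baseline adjustment. Per arm, with unit variances: var(Ȳ) = 1/n, var(X̄_obs) = 1/[n(1−m)], cov = ρ/n, and b ≈ ρ. Hence

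- arm-specific fill: V_a = 1 − ρ²(1−2m)/(1−m)
- arm-pooled fill: V_p = 1 − ρ²(1−m)
- difference: V_a − V_p = ρ²m²/(1−m), positive for any m > 0.

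**Step 3: what the model reports.** Replaced boys have residual variance 1 and the others 1−ρ², so the average residual variance is 1 − ρ²(1−m) = V_p. The standard error therefore reflects about V_p while the true variance is V_a. The two-sided 5% error is about 2Φ(−1.96/√(V_a/V_p)). This ignores a small leverage term and so runs slightly high.

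| m | ρ | V_a | V_p | V_a/V_p | approx. error |
|---|---|---|---|---|---|
| 20% | 0.5 | 0.812 | 0.800 | 1.02 | 5.2% |
| 20% | 0.7 | 0.633 | 0.608 | 1.04 | 5.5% |
| 30% | 0.5 | 0.857 | 0.825 | 1.04 | 5.4% |
| 30% | 0.7 | 0.720 | 0.657 | 1.10 | 6.1% |
| 50% | 0.5 | 1.000 | 0.875 | 1.14 | 6.7% |
| 50% | 0.7 | 1.000 | 0.755 | 1.32 | 8.9% |
| 60% | 0.7 | 1.245 | 0.804 | 1.55 | 11.5% |

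V_a is below 1 whenever m < 50%, equals 1 at 50% for any ρ, and exceeds 1 only beyond that.

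**Step 4: simulation with strata** (no true effect, 73:37). Across runs, arm-specific error was about 5% at 20% replaced, about 5.5-6% at 30% and about 6-8% at 50%. The arm-pooled fill stayed near 5%. Variance with the arm-specific fill was about 4-11% larger at 30% and 17-33% larger at 50%. Single runs scatter a little more widely: one with 2,500 trials gave 6% (ρ 0.5) and 15% (ρ 0.7) at 30%, and 17% and 35% at 50%. The mean estimate was within about 0.01 SD of zero, so no bias was seen.

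**Step 5: the same boys replaced at both visits.** If month-18 scores stay arm-filled and only the screening fill is pooled, the result gets worse. At ρ 0.7 the SD of the estimate was 0.1706 against 0.1667 as planned at 20% replaced, a variance ratio of (0.1706/0.1667)² = 1.05. At 40% it was 0.2076 against 0.1919, a ratio of 1.17. Across settings the variance was 2-11% larger at 20-30% replaced and 10-31% larger at 50%.

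**The case against.** **Share and consequence.** The addendum speaks only of a number of cases, and Protocol 10.2 has the parent complete the form, which points to a low share. PODCI is supportive, without alpha control. This stands: at 20% or less the point is one of principle, and no main conclusion of the trial depends on it.

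**A stronger reading to avoid.** A reader might infer that adjusting for this covariate adds error instead of removing it. Measured against no adjustment, that needs more than half of the baselines replaced while month-18 scores are observed. The documents do not show this. Below 50% the adjustment still helps, only less than it should.

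**The obvious remedy is not free.** Boys may enter at 6, and a boy under 8.5 at screening is still under 10 at month 18. If he answers for himself both times, both scores are filled from the same Group 1 donors, and the plan is at least consistent, much like a complete-case ANCOVA. Pooling the screening fill alone breaks that match (step 5). This stands and shapes the fix.

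**The outcome fill matters more.** When the same boys' month-18 scores are filled too, simulated error at ρ 0.7 reached 12% at 20% replaced and 24% at 40%, mostly from the outcome fill. True, but the baseline defect remains where the outcome is genuine.

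**An unseen file note.** The addendum also amends a PODCI note of 23 May 2022 that is not available. It might cover baseline or cells without donors, but the addendum's own text makes no exception.

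**Conclusion.** The point holds. As written, Change 1 sets some pre-randomisation PODCI scores, including recorded ones, by assigned arm. The consequence is lost precision and a standard error that is too small. It is not bias: none is expected if replacement is unrelated to score.

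With month-18 scores observed, the size is negligible at 20% replaced, modest at 30% and material at 50%, as in step 4. The result rests on the assumed correlation, on the assumed stratum shares and above all on the share replaced, which the documents do not report. That missing count decides whether the matter is trivial or worth acting on. The concern is confined to an exploratory endpoint with nominal p-values.

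**What to change.** In Addendum 2.1:

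- Analyse the month-18 change on boys with a genuine Group 1 month-18 score.
- For these boys, drop treatment from the imputation cell at screening: fill Group 2 or missing screening scores with the Group 1 screening mean for the steroid stratum and target/off-target group, pooled over arms.
- Do not pool the screening fill while keeping arm-mean-filled month-18 outcomes in the same analysis.
- Report the number of screening and month-18 scores replaced, by arm.
- State a fallback for cells without a donor; the addendum has none. Under assumed stratum shares, an arm-by-stratum cell had no Group 1 donor in 3-13% of simulated trials at 20-40% replaced. Pooling over arms makes this rare.

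In simulation, this combination was never materially worse than the plan, whatever the overlap between boys replaced at screening and at month 18.

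The cost is one grouping variable, one restriction and a count table, with no new data. Boys without a genuine month-18 score leave this exploratory analysis; the planned version can stay as a sensitivity analysis that includes them. If outputs already exist, a supplementary table is enough.
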